5.2.1 Missing or Partial Dates

In general, imputation of partial missing dates will be made for AE onset date, start and end dates of concomitant therapy, and date of initial diagnosis of UC.

For AE onset date, the global standard AE imputation rules listed below will be applied.

- Partial AE onset dates will be imputed as follows:
 - If the onset date of an adverse event is missing day only, it will be set to:
 - First day of the month that the AE occurred, if month/year of the onset of AE is different than the month/year of the first dose date;
 - The day of first dose date, if the month/year of the onset of AE is the same as month/year of the first dose date and month/year of the AE resolution date is different;
 - The day of first dose date or day of AE resolution date, whichever is earliest, if month/year of the onset of AE and month/year of the first dose date and month/year of the AE resolution date are same
 - If the onset date of an adverse event is missing both day and month, it will be set to the earliest of:
 - January 1 of the year of onset, as long as this date is after the first dose date;
 - Month and day of the first dose date, if this date is the same year that the AE occurred;
 - The AE resolution date
 - Completely missing onset dates will not be imputed.
- Partial AE resolution dates not marked as ongoing will be imputed as follows:
 - If the resolution date of an adverse event is missing day only, it will be set to the earliest of the last day of the month of occurrence of resolution or the day of the date of death, if the death occurred in that month;
 - If the resolution date of an adverse event is missing both day and month, it will be set to the earliest of December 31 of the year or the day and month of the date of death, if the death occurred in that year;
 - Completely missing resolution dates will not be imputed;

For start and end dates of concomitant therapies, the global standard AE imputation rules listed above will be applied accordingly.

For date of initial diagnosis of UC, the following rule will be applied.

- If date is completely missing, no imputation will be made;
- If year is missing, no imputation will be made;
- If only year is present, but month and day are missing, then June 30th will be used;
- If only day is missing but year and month are available, then the 15th of the month will be used;

However, the above imputations will be modified by the following rules:

- If such imputed date for initial diagnosis is on or after study consent date, then consent date - 1 will be used.

5.3 Software

All report outputs will be produced using Statistical Analysis System (SAS[®]) version 9.2 or a later version in a secure and validated environment.

5.4 Study Patients

5.4.1 Disposition of Patients

A clear accounting of the disposition of all patients who enter the study will be provided, from screening to study completion.

Following summaries will be provided.

- A summary of the number of patients screened for entry into the study and the number and percentage of patient screen failures by major reason and overall (Analysis set: All Patients)
- A summary of the number of patients enrolled per center, and per country if appropriate [Analysis set: All Patients in intent to treat (ITT) population]
- A summary of the number of patients enrolled, the number and percentage of patients treated (with at least one dose of study medication) and the number and percentage of patients entering, withdrawing from study treatment, withdrawing from the study and completing each visit. Withdrawals from study treatment and from the study should also be summarized by major reason.

By-patient listings of visit dates and withdrawal/study completion details (including reason for discontinuation and duration of treatment prior to discontinuation) should be provided.

5.4.2 Protocol Deviations

Major protocol deviations are defined as those deviations from the protocol likely to have an impact on patient's right, safety, well-being and/or the validity of data for analysis.

Major protocol deviations and any action to be taken regarding the exclusion of patients or affected data from specific analyses are defined in the project-specific Protocol Deviation Specification. The final determination of major protocol deviations and the exclusion of patients from any of the analysis sets will be made prior to database lock.

A summary of the number and percentage of patients with a major protocol deviation as well as by type of deviation will be provided. Also, a by-patient listing of all protocol deviations will be provided. The patients whose PDs related to Covid-19 pandemic will also be included in the listings.

5.5 Data Conventions and Analysis Sets

Unscheduled assessments (laboratory data, ECG, or vital signs associated with non-protocol clinical visits or obtained during investigating or managing adverse events) will be included in listings, but not summaries. If more than one laboratory value is available for a given visit, the last valid observation will be used in summaries and all observations will be presented in listings. If it is not possible to determine which is the first measurement due to missing times, then the average of all measurements for that time point will be used as the value for that time point.

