2.3 BENEFIT - RISK ASSESSMENT

With this novel mechanism of action Neihulizumab is anticipated to be effective in treating T-cell mediated autoimmune diseases. In both Studies 2012.005.01 and 2014.002.01, signs of efficacy were clearly observed for psoriasis. Study 2014.009.01 also demonstrated clinical efficacy for psoriatic arthritis (see [Section clinical studies](#)). Patients of UC might benefit from the trial because T cells play a pivotal role in the pathogenesis of UC, and based on Neihulizumab's novel mechanism of action it is expected that patients with UC are going to benefit from the treatment of Neihulizumab.

Risk of hematopoietic cell depletion

In Study 1304.1, Study 2012.005.01, Study 2014.002.01 and Study 2014.009.1, Neihulizumab single or multiple doses were well tolerated. No cytokine release syndrome or hematopoietic cell depletion was observed in these four studies. A mild, clinically insignificant, transient, and reversible decrease in the mean and median total leukocyte counts was observed in the 3 mg/kg group in trial 2012.005.01 and in the 6 mg/kg and 9 mg/kg groups in trial 2014.002.01, and in study 2014.009.01 where 7 doses of Neihulizumab at 9 mg/kg were administered. Although the risk that Neihulizumab will affect stem cells is convincingly low, it is still critical that careful long-term monitoring of peripheral blood cells is carried out to rule out a clinically significant adverse effect of Neihulizumab on bone marrow stem cells *in vivo*.

Risk of impaired immune function

Neihulizumab has been demonstrated to induce apoptosis selectively in late stage activated T-cells. This selectivity suggests that naïve and resting memory T-cells would be spared from deletion by Neihulizumab, and therefore that Neihulizumab may be less immunosuppressive than pan-T-cell depleting mAbs or the systemic immunomodulating agent such as cyclosporine. However, it cannot be ruled out that depletion of activated T-cells by Neihulizumab may lead to a transiently increased risk of infection. This risk will be addressed by clinical monitoring for adverse events during the treatment and observation periods.

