7.1.2 Safety analyses

Safety analyses will be performed based on the mITT set. No hypothesis testing is planned prospectively.

Adverse events will be coded using the Medical Dictionary for Drug Regulatory Affairs (MedDRA). Adverse events occurring prior to drug administration will be assigned to the screening period. All other adverse events will be assigned to the treatment periods for evaluation.

Independent of this rule, the relationship of an adverse event to the study drug treatment will be assessed by the investigator. The evaluation of adverse events will comprise various frequency tabulations.

Descriptive statistics of demographic data, of time-courses and of changes from baseline of vital signs and physical examination will be provided.

Descriptive statistics of laboratory values over time and for the difference from baseline will be provided. Frequency tables of changes with respect to the reference range between baseline and last value on treatment will also be presented.

Relevant findings in ECG measurements will be reported under “Relevant Medical History /Baseline Conditions” (at screening).

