5.5.2 Visit Windows

‘Baseline’ is defined as the last available pre-treatment assessment. ‘End of Study’ is defined as the last available post-treatment assessment. ‘Treatment Day’ will be calculated relative to the date of first dose i.e. Treatment Day = Assessment Date –First dose date + 1.

The visit windows and study relative days are given in below table. Assessments at early termination and any deviation of scheduled visits will be slotted based on the following visit window but unscheduled visits will not be slotted to analysis visit as below.

Period	Analysis Visit Protocol Amendments 1-4	Analysis Visit Protocol Amendments 1-3	Analysis Visit Protocol Amendment 4	Target day (relative to first dose date)	Study Day** ranges
Screening Period	Week -4 to -1	Week -4 to -1	Week -4 to -1		-28 to -1
Treatment Period	Week 0	Week 0	Week 0	1	<=1
	Week 1	Week 1	Week 1	8	2-11
	Week 2	Week 2	Week 2	15	12-18
	Week 3	Week 3	Week 3	22	19-25
	Week 4	Week 4	Week 4	29	26-32
	Week 5		Week 5	36	33-39
	Week 6	Week 6	Week 6	43	40-47
	Week 7		Week 7	50	48-53
	Week 8	Week 8		57	54-60
	Week 9		Week 9	64	61-67
EOT	Week 12	Week 12	Week 12	84	82-104
Follow-up	Week 16	Week 16	Week 16	112	105-132
	Week 20	Week 20	Week 20	140	133-174
EOS	Week 26	Week 26	Week 26	182	175-212

**Study Day=Visit Date-First dose Date+1

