5.10.4 Clinical Laboratory Evaluation

Laboratory results will be summarized using standard international (SI) units, as appropriate. For all quantitative parameters listed in 3.2.2.2, the actual value and the change from baseline to each post-baseline visit and to the EOT will be summarized by visit using descriptive statistics. Qualitative parameters listed in 3.2.2.2 will be summarized using frequencies (number and percentage of patients), and changes from baseline to each post-baseline visit and to the EOT will be reported using shift tables. Percentages will be based on the number of patients with both non-missing baseline and relevant post-baseline results.

Laboratory test results will be assigned a low/normal/high (LNH) classification according to whether the values are below (L), within (N), or above (H) the laboratory parameter's reference range. Similar shift tables will be used to compare the baseline LNH classification to the LNH classification for the highest and lowest value during the treatment period.

A by-patient listing of laboratory will be provided with abnormal values flagged.

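### The SAP's worst-value laboratory and vital-sign tables can miss the true extreme, because unscheduled and superseded repeat results are kept out of all summaries and the period covered is undefined

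*SAP*

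**What the plan says.** **Unscheduled values.** SAP 5.5 covers laboratory, ECG and vital-sign assessments outside protocol visits. It states that these, including those "obtained during investigating or managing adverse events) will be included in listings, but not summaries". SAP 5.5.2 adds that "unscheduled visits will not be slotted to analysis visit as below".

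**Repeat values.** For several laboratory results at one visit, SAP 5.5 says that "the last valid observation will be used in summaries and all observations will be presented in listings". The tie-break then reads "If it is not possible to determine which is the first measurement due to missing times, then the average of all measurements". It is worded for the first result, although the rule uses the last.

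**Laboratory tables.** SAP 5.10.4 plans by-visit summaries, in which "the actual value and the change from baseline to each post-baseline visit and to the EOT will be summarized by visit using descriptive statistics". It also plans shift tables from the baseline low/normal/high (LNH) class to the "LNH classification for the highest and lowest value during the treatment period". The treatment period is not defined there.

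**Vital signs.** SAP 5.10.5 plans a separate summary of each patient's maximum, minimum and change to each.

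**Why blood counts matter here.** Protocol 2.3 discusses haematopoietic cell depletion under its own risk heading. It says that "it is still critical that careful long-term monitoring of peripheral blood cells is carried out".

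**The concern.** A highest/lowest-value table exists to show how far each patient moved at worst. Samples taken because a patient is unwell, or because a first result looked abnormal, are an obvious place for that worst value to occur. SAP 5.5 removes the first kind from every summary. It also removes any repeated result that is not the last valid one. As written, the worst-value table is built from a set that may not contain the worst value.

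Safety is the secondary objective, and falls in white-cell counts were seen in earlier studies, including at the 9 mg/kg dose used here. With at most 40 patients planned and enrolment closed early (SAP 4.1), one or two patients could change what the shift table shows.

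**Working it through.** The plan states no figure on this point, so there is none to reproduce. The check traces each kind of laboratory value through the rules and then counts visits.

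**1. Which values reach which output** (SAP 5.5, 5.5.2, 5.10.4)

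| Laboratory value | By-visit summary | Highest/lowest LNH shift | Listing |
|---|---|---|---|
| Scheduled, single result, up to Day 84 | yes | yes | yes |
| Scheduled, single result, Days 112, 140, 182 | yes | no, under the SAP 5.5.2 labels | yes |
| Repeat at a visit, not the last valid one | no | no | yes |
| Unscheduled | no | no | yes |

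If times are missing, the repeats are averaged, so the lowest result does not enter as itself. For vital signs only the unscheduled exclusion applies, because the repeat rule is written for laboratory values.

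**2. A hypothetical patient.** Neutrophils are in range at the scheduled Day 43 visit, 0.4 x 10^9/L in an unscheduled Day 46 sample taken during an infection, and in range again on Day 50. Day 46 lies inside the Week 6 window (Days 40-47), but an unscheduled visit is not slotted. If all other scheduled results are in range, the patient is classed normal to normal in the shift table. The infection is tabulated as an adverse event. The count is tabulated only if the investigator records it as an event too.

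**3. Scheduled laboratory visits after Day 84** (Protocol Table 1; SAP schedule for Amendments 1-3)

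- Amendment 4: Days 8, 15, 22, 29, 36, 43, 50, 64, 78, 84, 112, 140, 182, which is 13 post-baseline visits. Three fall after Day 84: 3/13 = 23%.
- Amendments 1-3: Days 8, 15, 22, 29, 43, 57, 71, 84, 112, 140, 182, which is 11 visits. Three fall after Day 84: 3/11 = 27%.

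The window table in SAP 5.5.2 labels Weeks 16 and 20 as follow-up and Week 26 as end of study, so these three lie outside its treatment period. It also gives Week 12 its own end-of-treatment label. Day 84 is counted as inside here, but the text does not settle it.

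**4. Room for a dip between scheduled samples.** The intervals in days, starting from Day 1, are:

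- Amendment 4: seven of 7, then 14, 14, 6, 28, 28, 42.
- Amendments 1-3: four of 7, then 14, 14, 14, 13, 28, 28, 42.

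A fall that begins and recovers inside one of the longer intervals could be seen only in an unscheduled sample.

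**The case against.** The strongest reply is that other outputs cover most of this.

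- **Adverse-event tables.** Protocol 5.2.5.4 has laboratory changes recorded as adverse events when the investigator judges them clinically relevant. They then enter the treatment-emergent and Grade 3 or higher tables of SAP 5.10.2. Infections have their own summary under SAP 5.10.3.
- **By-visit summaries.** These run through Weeks 16, 20 and 26 and, under SAP 5.2, include the minimum. The earlier signal was a mild fall in mean and median white-cell counts, which such summaries would show.
- **Context.** Protocol 2.3 reports no haematopoietic depletion in four earlier studies and rates the stem-cell risk as low. It asks for monitoring and does not prescribe a form of table.
- **Listings.** Every value is listed and abnormal ones are flagged, so patient-level review is practical at this size.
- **Period.** The schedule table is titled as covering the treatment period and runs to Day 182, so the shift table might be meant to cover follow-up.

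Most of this stands, and it narrows the point. It does not repair the worst-value tables. The adverse-event route depends on a judgement of relevance for each result. By-visit minima come from the same restricted set of values and do not count the patients who fell. Listings give no frequencies. The two possible meanings of the treatment period are themselves a reason to define it.

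**Conclusion.** The concern holds in a limited form. The SAP sets a rule that works against the purpose of its own worst-value tables and leaves their period undefined. The values lost from every summary table are those found only in an unscheduled or superseded sample and not recorded as an adverse event. How many there will be cannot be derived from the documents. The period limit affects 3 of 13 or 3 of 11 scheduled visits, in the shift table only, and only if the SAP 5.5.2 labels apply. Severity is minor to moderate.

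A reader might infer more, but the documents do not support it:

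- **That low counts vanish from all tables.** This is true only of the subset just described.
- **That over half of follow-up is unsummarised.** Days 85-182 are 98 of 182 days (54%), but that is calendar time, and the scheduled results in it are tabulated by visit.
- **That the last repeat is usually a recovered value, so the tables lean towards no change.** Nothing in the documents shows this. A repeat may be lower, or may replace an invalid sample.
- **That the Protocol 7.1.2 table, which compares values "between baseline and last value on treatment", is a current fault.** It is an additional table there, and the SAP goes further by planning a worst-value shift.

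**What to change.** 1. In SAP 5.5, confine the exclusion of unscheduled values and the last-valid-repeat rule to by-visit summaries.
2. In SAP 5.10.4 and 5.10.5, state that highest/lowest and maximum/minimum tables use all valid values after the first dose (scheduled, unscheduled and repeat) through Day 182.
3. Define the treatment and follow-up periods for these tables, say where Day 84 belongs, and show worst values for each period.
4. Correct the tie-break in SAP 5.5 so that it refers to the same result as the rule it serves.

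Shifts by CTCAE v4.03 grade for key blood counts would add depth that LNH classes lack. They are optional, since the documents apply CTCAE to adverse events only.

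The cost is SAP wording and a few more programmed tables, on data already collected. Abnormality rates may look slightly less favourable.

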5.5.1 Analysis Sets

The study populations include the ITT, modified ITT (mITT), safety, and PK sets.

Intent-to-Treat Set: The ITT population is defined as all patients who are enrolled irrespective of treatment received or not.

Modified Intent-to-Treat Set: The mITT set is defined as all patients who are enrolled and have received at least one dose of Neihulizumab treatment.

The efficacy analyses will be based on the modified ITT set. Summaries of patient disposition, demographics, and disease characteristics, assessments of physical condition and functionality, and dosing of study drug will be provided in this population.

Safety Set: Safety set includes all patients in mITT. This analysis set will be used for all safety analyses and analysis of exposure.

Pharmacokinetic Set: This set will include all patients in mITT who provide at least one post-baseline evaluable drug concentration value.

5.5.2 Visit Windows

‘Baseline’ is defined as the last available pre-treatment assessment. ‘End of Study’ is defined as the last available post-treatment assessment. ‘Treatment Day’ will be calculated relative to the date of first dose i.e. Treatment Day = Assessment Date –First dose date + 1.

The visit windows and study relative days are given in below table. Assessments at early termination and any deviation of scheduled visits will be slotted based on the following visit window but unscheduled visits will not be slotted to analysis visit as below.

Period	Analysis Visit Protocol Amendments 1-4	Analysis Visit Protocol Amendments 1-3	Analysis Visit Protocol Amendment 4	Target day (relative to first dose date)	Study Day** ranges
Screening Period	Week -4 to -1	Week -4 to -1	Week -4 to -1		-28 to -1
Treatment Period	Week 0	Week 0	Week 0	1	<=1
	Week 1	Week 1	Week 1	8	2-11
	Week 2	Week 2	Week 2	15	12-18
	Week 3	Week 3	Week 3	22	19-25
	Week 4	Week 4	Week 4	29	26-32
	Week 5		Week 5	36	33-39
	Week 6	Week 6	Week 6	43	40-47
	Week 7		Week 7	50	48-53
	Week 8	Week 8		57	54-60
	Week 9		Week 9	64	61-67
EOT	Week 12	Week 12	Week 12	84	82-104
Follow-up	Week 16	Week 16	Week 16	112	105-132
	Week 20	Week 20	Week 20	140	133-174
EOS	Week 26	Week 26	Week 26	182	175-212

**Study Day=Visit Date-First dose Date+1

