Lead Investigator's Name (Print)

06 Nov 2018

Lead Investigator's Signature

Date of Signature
(DD MMM YYYY)

ACKNOWLEDGE STATEMENT INVESTIGATOR(S)

Each participating investigator must agree to the approved Clinical Study Protocol and any subsequent amendment(s) by signing the Investigator Clinical Study Protocol Agreement Form.

TABLE 1 (Scheduled Events of Treatment Period)

Trial Periods	Screening V1	V 2	V 3	V 4	V 5	V 6	V 7	V 8	V 9	V 10	V 11	V 12	V 13	V 14	V 15
Day	-28 to -1	1	8	15	22	29	36	43	50	64	78	84 EOT ¹	112	140	182 EOS
Week	-4 to -1	0	1	2	3	4	5	6	7	9	11	12	16	20	26
Time window (days)	N.A.	±0	±1	±1	±1	±1	±1	±1	±1	±1	±1	±2	±4	±4	±4
Informed Consent	x														
Check of Eligibility	x														
Patient Medical History	x														
Patient Ulcerative Colitis History	x														
Inclusion/Exclusion Criteria	x	x													
Concomitant Therapy ²	x	x	x	x	x	x	x	x	x	x	x	x	x	x	x
Assess for Adverse Events		x	x	x	x	x	x	x	x	x	x	x	x	x	x
Demographics/Weight	x	x ³													
Full Physical Examination	x	x										x			x
Partial Physical Examination			x	x	x	x	x	x	x	x	x		x	x	
Vital Signs	x	x	x	x	x	x	x	x	x	x	x	x	x	x	x
12-Lead Resting ECG	x														
Flexible sigmoidoscopy ⁴	x ⁵											x			x
Administer AbGn-168H		x	x	x	x	x	x	x	x	x	x				
Diary Instruction/review	x														
Diary collection/review	x	x	x	x	x	x	x	x	x	x	x	x	x	x	x
Physician Global Assessment	x	x	x	x	x	x	x	x	x	x	x	x	x	x	x
Complete Mayo Clinic score ⁴	x											x			x
Partial Mayo Clinic score ⁶		x	x	x	x	x	x	x	x	x	x		x	x	
Histopathological analysis	x ⁷											x			x
Inflammatory Bowel Disease Questionnaire (IBDQ)	x											x			x
Stool screening ⁸	x														
Fecal calprotectin and CRP	x					x				x		x	x	x	x
PK sampling ⁹		x	x	x	x	x	x	x	x	x	x	x	x	x	
ADA		x				x				x		x	x	x	x
Safety Lab Tests (Hematology and Chemistry)	x	x	x	x	x	x	x	x	x	x	x	x	x	x	x
Urinalysis ¹⁰	x	x	x	x	x	x	x	x	x	x	x	x	x	x	x
HbA1c test	x														
QuantiFERON® test for tuberculosis	x														
Pregnancy/Hormone Test ¹¹	x	x	x	x	x	x	x	x	x	x	x	x			x
Drug Screening ¹²	x														
Viral screening	x														

Footnotes:

1. Patients who completed the treatment (10 doses) should continue in the study and attend visits through EOS. Patients who discontinue before the completion of 10 doses will be encouraged to continue the visit until EOS. If patients are unable to continue the visits until EOS, the last visit should be considered as EOS and EOS assessments should be completed.

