4 INVESTIGATIONAL PLAN

4.1 Overall Study Design and Plan

This is a single arm, open label, multiple dose, multi-center study to be conducted in 12-18 centers in United States (US) in 30-40 patients with a diagnosis of moderate to severe active ulcerative colitis, refractory or intolerant to anti-TNF α and/or anti-integrin treatments. Due to the COVID-19 pandemic, the holding of patient enrollment, as well as slow patient enrollment prior to the pandemic, the study has been closed out and the data will be analyzed at this time. Therefore, only available data from the patients will be included in the analysis.

Per protocol amendment 4, a total of 10 doses of Neihulizumab at 9 mg/kg will be administered to patients over 12 weeks on Day 1 (Week 0), Day 8 (Week 1), Day 15 (Week 2), Day 22 (Week 3), Day 29 (Week 4), Day 36 (Week 5), Day 43 (Week 6), Day 50 (Week 7), Day 64 (Week 9), and Day 78 (Week 11).

Whereas the patients enrolled under Protocol amendments 1-3, a total of 8 doses of Neihulizumab at 9 mg/kg are administered on Day 1 (Week 0), Day 8 (Week 1), Day 15 (Week 2), Day 22 (Week 3), Day 29 (Week 4), Day 43 (Week 6), Day 57 (Week 8), and Day 71 (Week 10).

Patients will be followed up on Day 84 (Week 12, End of Treatment, primary endpoint), Day 112 (Week 16), Day 140 (Week 20) and Day 182 (Week 26, End of Study) after the first dose of Neihulizumab.

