4.2 Endpoints

4.2.1 Efficacy Variables

Efficacy will be assessed by cMCS, pMCS, endoscopy, biopsy, Inflammatory Bowel Disease Questionnaire (IBDQ), and Biomarkers (faecal calprotectin and c-reactive protein).

The **primary efficacy endpoint** is proportion of clinical responders at Week 12.

The clinical responder is defined as a \geq 3-point reduction in MCS, a 30% or greater decrease from the baseline score, and with a 1-point or greater decrease of the rectal bleeding subscale or an absolute rectal bleeding score of 0 or 1 at Week 12.

Secondary efficacy endpoints are:

1. The proportion of patients with clinical response at Weeks 6, 7, 9 and 11 defined as a ≥ 2 -point decrease in pMCS, and with a 1-point or greater decrease of the rectal bleeding subscale or an absolute rectal bleeding score of 0 or 1.
2. The proportion of patients with clinical remission, defined as MCS of 2 or lower (or pMCS of 1 or lower) and no subscore higher than 1 at Weeks 6, 7, 9, 11 and 12.
3. The proportion of responders who remain in clinical response and remission at Weeks 16, 20, and 26.
4. Flexible sigmoidoscopy subscore changes from baseline at Weeks 12 and 26.
5. The proportion of patients with sigmoidoscopic improvement, defined as any decrease in MCS endoscopic subscore, at Week 12 and 26.
6. The proportion of patients with mucosa healing defined as an absolute subscore for endoscopy of 0 or 1 at Weeks 12 and 26.
7. Change of histological activity grade from baseline at Weeks 12 and 26 using the Geboes system.
8. The proportion of patients with histological healing defined as histological grade = 0 at Weeks 12 and 26.
9. Change of Inflammatory Bowel Disease Questionnaire (IBDQ) from baseline at Weeks 12 and 26.
10. The proportion of patients with IBDQ response, defined as an increase from baseline of at least 16 points at Weeks 12 and 26.

Above time points are for the patient enrolled under Protocol Amendment 4. The time points for the patient enrolled under Amendments 1-3 are given in the table in the SAP section 4.5.2 as well as in Appendix 1 'Schedule of Assessments (Protocol Amendment 1-3)' and Appendix 2 'Schedule of Assessments (Protocol Amendment 4)'.

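### The SAP visit-window table has no Week 10 or Week 11 row, so early-termination or off-schedule assessments on Days 68–81 have no analysis visit and would be scored as non-response

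*SAP*

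**What the plan says.** SAP 5.5.2 sets the rule for placing assessments: "Assessments at early termination and any deviation of scheduled visits will be slotted based on the following visit window". Visits that were never on the schedule are not placed at all. The table that follows gives one Study Day range per analysis visit, with columns showing which visits apply under Amendments 1–3 and under Amendment 4. Its last treatment-period row is Week 9 (target Day 64, Days 61–67). The next row is Week 12 (target Day 84, Days 82–104).

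SAP 4.1 schedules a dose on Day 71 (Week 10) under Amendments 1–3 and on Day 78 (Week 11) under Amendment 4. The schedules of assessments place a partial Mayo score at both visits.

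In SAP 4.2.1, secondary endpoint 1 is "The proportion of patients with clinical response at Weeks 6, 7, 9 and 11", and secondary endpoint 2 (remission) uses the same weeks plus Week 12. For patients enrolled earlier, the same section says: "The time points for the patient enrolled under Amendments 1-3 are given in the table in the SAP section 4.5.2". It then adds the schedules of assessments as a second source. The section number cited does not exist in the SAP; the table is in 5.5.2.

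SAP 5.9.1.1 counts a missing primary or secondary binary value as non-response and adds a supportive analysis of observed data. SAP 5.2 reports the two amendment groups separately.

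**The concern.** Week 11 is a named time for two secondary endpoints, and Week 10 is its counterpart for patients on the earlier schedule. The table that assigns early-termination and deviated visits has no place for either. A patient with a real partial Mayo score on one of the uncovered days would have no Week 10 or Week 11 value in the dataset and would then be counted as a failure. That would be an error of bookkeeping, not an outcome.

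Such visits are foreseeable. Protocol 4.2 allows an infusion to be delayed by up to 10 days, and Protocol 3.3.4.1 requires withdrawal from treatment on worsening. By-visit laboratory and vital-sign summaries would have the same hole. The groups are analysed separately in a trial that SAP 4.1 says closed early after slow enrolment, so a single misplaced patient can move a percentage visibly.

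**Working it through.** The plan gives no figure to reproduce here. The check compares the printed ranges with the calendar.

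**Step 1. Coverage, all rows together (SAP 5.5.2).** Ranges: up to 1, 2–11, 12–18, 19–25, 26–32, 33–39, 40–47, 48–53, 54–60, 61–67, 82–104, 105–132, 133–174, 175–212. Each range starts the day after the previous one ends, except between 67 and 82. Uncovered: Days 68 to 81, that is 81 − 68 + 1 = 14 days.

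**Step 2. Scheduled visits near the gap (tolerances from the schedules of assessments).**

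| Visit | Group | Target and tolerance | Days | Window |
|---|---|---|---|---|
| Week 9 | 2 | 64 ± 1 | 63–65 | Week 9 |
| Week 10 | 1 | 71 ± 1 | 70–72 | none |
| Week 11 | 2 | 78 ± 1 | 77–79 | none |
| Week 12 | both | 84 ± 2 | 82–86 | Week 12 |

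**Step 3. Which off-schedule visits fall in the gap.**
- Group 1, Week 10: 2–3 days early (Days 68–69) or 2–10 days late (Days 73–81).
- Group 2, Week 11: 2–3 days late (Days 80–81), or 2–10 days early (Days 68–76).
- Group 2, Week 9: 4–10 days late (64 + 4 = 68 to 64 + 10 = 74).
- Either group: any early-termination assessment on Days 68–81.

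**Step 4. Coverage by amendment column.**

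| Column | Uncovered as printed | Still uncovered if only Week 10 (68–74) and Week 11 (75–81) are added |
|---|---|---|
| Amendment 4 | 54–60, 68–81 | 54–60, 68–74 |
| Amendments 1–3 | 33–39, 48–53, 61–81 | 33–39, 48–53, 61–67, 75–81 |

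**Step 5. Do two rows fit the gap?** The midpoints between target Days 64, 71, 78 and 84 are 67.5, 74.5 and 81. They give Week 10 = Days 68–74 and Week 11 = Days 75–81, which meet the printed Week 9 end (67) and Week 12 start (82) exactly.

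**Step 6. Effect of one unplaced responder.** With r responders out of n, the reported rate falls from r/n to (r − 1)/n, a drop of 100/n percentage points. Group sizes are not given. For an assumed n of 20 the drop is 5 points; for n of 5 it is 20 points. In the observed-data analysis the patient leaves both numerator and denominator at that visit, so the response is still not counted.

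**Step 7. Worst case, if every visit were placed by window.** Week 11 response would be 0/n, with an upper 95% Clopper-Pearson limit of 1 − 0.025^(1/n): 16.8% for n = 20, 11.6% for n = 30 and 8.8% for n = 40. The last two use the planned size of the whole trial, so they are larger than a single group would be.

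**The case against.** **The rows may exist.** The gap is exactly the width of two 7-day rows, and the bounds on either side look as if they were set with Weeks 10 and 11 in mind. The rows could have been lost when the PDF was converted to text; the Amendment 4 schedule in the SAP appendix shows conversion damage. This cannot be excluded. Against it, the adjoining rows and the footnote are intact and nothing marks a break. A typing omission would look the same.

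**A reader might infer that all Week 10 and Week 11 data are lost.** The documents do not support that. The slotting rule covers early-termination assessments and deviations from scheduled visits. An on-time Day 71 or Day 78 visit is neither, and most naturally keeps its nominal label, although the SAP does not say so.

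**A reader might also infer that Week 10 is defined nowhere.** It is defined: SAP 4.1 and the Amendments 1–3 schedule both give Day 71 as Week 10, and SAP 4.2.1 cites the schedules alongside the window table. What is missing is the window row.

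**The impact is limited.** The primary endpoint uses the complete Mayo score at Week 12, whose window is intact. The change endpoints are assessed at Weeks 12 and 26. Endpoints 1 and 2 are descriptive proportions with confidence intervals. All of this stands.

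**The observed-data analysis is a safeguard.** Only in part: it avoids scoring the unplaced value as failure, but it does not use the value.

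**Conclusion.** The point holds for early-termination and off-schedule assessments. On the table as printed, those falling on Days 68–81 have no analysis visit. At Week 11 in Group 2 (secondary endpoints 1 and 2), and at the parallel Week 10 time in Group 1, the patient would be scored as a non-responder despite having been assessed.

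The effect is 100/n percentage points for each true responder affected. How many patients are affected cannot be known from the documents. Loss of every Week 10/11 value is a worst case that would need on-time visits to be placed by window too. The primary endpoint is unaffected.

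The conclusion assumes that the printed table is complete. If the signed SAP contains the two rows, what remains is the gaps within each amendment column and the missing statement on how on-schedule visits are labelled. The point should be fixed, but it does not threaten the trial's main result.

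**What to change.** 1. Check the table in the signed SAP. If the Week 10 and Week 11 rows are there, go to item 3 and the column check in item 2.
2. If they are absent, add Week 10 (Amendments 1–3, target Day 71, Days 68–74) and Week 11 (Amendment 4, target Day 78, Days 75–81). Better, give contiguous ranges within each amendment column, since two rows alone leave the days shown in step 4. One way is to use midpoints between each column's own targets, with the midpoint day going to the earlier visit:
   - Amendment 4: (50 + 64)/2 = 57, (64 + 78)/2 = 71 and (78 + 84)/2 = 81. This gives Week 7 = 48–57, Week 9 = 58–71, Week 11 = 72–81.
   - Amendments 1–3: (29 + 43)/2 = 36, (43 + 57)/2 = 50 and (57 + 71)/2 = 64. This gives Week 4 = 26–36, Week 6 = 37–50, Week 8 = 51–64, Week 10 = 65–81. The last range runs past the midpoint of 77.5 so that the Week 12 window still starts on Day 82.
3. State that on-schedule visits are analysed by nominal visit, and that windows apply only to early-termination and deviated visits.
4. List Group 1's on-treatment secondary times as Weeks 6, 8 and 10, in line with its schedule, and correct the section and appendix numbers cited in SAP 4.2.1.

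The cost is two rows, or a few changed ranges, plus two sentences. No new data are needed. Because the study is open-label and already closed, the change should be dated and documented before the windows are applied to the data.
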